1. SYNOPSIS

Study Title	The development and pilot testing of a new Magnetic Resonance (MR) imaging					
	protocol to quantify both myeloma disease burden and associated bone loss					
Internal ref. no. / short title	LOOMIS- myeLOma bOne MrI Study					
Study Design	Observational Prospective Cohort					
Study Participants	Group 1- Myeloma					
	Group 2- Monoclonal Gammopathy of Unco	ertain Significance (MGUS)				
	Group 3- Healthy Volunteers					
Planned Sample Size	60					
	Group 1- Myeloma- 34					
	Group 2- MGUS - 13					
	Group 3 - Healthy Volunteers - 13					
Planned Study Period	September 2017 – December 2021					
	Objectives	Outcome Measures				
Primary	To develop and pilot test a novel	Novel imaging based endpoints:				
	Magnetic Resonance (MR) imaging	1. DW-MRI (Diffusion Weighted-				
	protocol with the aim to accurately: 1. Quantify tumour burden	Magnetic Resonance Imaging): ADO (apparent diffusion coefficient)				
	2. Quantify bone loss	change (Pawlyn et al , 2016)				
	2. Quantity bone loss	2. Total spinal 'hole' volume				
		3. Total spine 'collapse' volume				
		4. FSA (Fine Structural Analysis):				
		trabecular wall thickness (Rafferty				
		et al, 2016)				
		Correlate endpoints:				
		Bone density (DXA imaging)Serum CTX-1				
		Serum P1NP				
		Further experimental serum				
		biomarkers of myeloma				
	bone disease					
Secondary	To pilot test a novel MR imaging protocol with the aim to accurately:	1 and 2 - Repeat quantification of endpoint parameters after induction				
	Detect longitudinal changes in	therapy and best response achieved				
	tumour load with therapy	by IWMG criteria or at treatment				
	2. Detect longitudinal changes in	failure				
	bone microarchitecture with					
	therapy					
	3. Assess participants Quality of					
	Life (EQ-5D) throughout the					
	study					

4.	Assess participants experience of	3 – Analyse participants quality of
	the novel MR imaging scan	life using data from the EQ-5D-5L
		questionnaire
		4- Analyse participants experience
		of the novel MR imaging using data
		from MRI/DXA scanning
		questionnaire

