5. STUDY DESIGN

This novel MR protocol is developing new metrics and combining elements that have not previously been combined therefore, there will be a protocol development phase prior to trial recruitment in which a group of healthy volunteers will be scanned to ensure timings and data collection is optimized. This phase will take place prior to trial start and is not included as part of this protocol, as it is already covered by REC approval for OCMR protocol development.

Once the protocol development phase has been completed, 60 subjects will be recruited to take part in this study; Group 1: Myeloma, (n=34), Group 2: MGUS, (n=13) and Group 3: Healthy age-matched volunteers, (n=13). Participants from Groups 1 and 2 will be identified and approached by a healthcare professional in the oncology clinic at the Churchill Hospital, Oxford. Group 3 participants will usually be the partners of the participants from group 1 and 2, and they will be recruited alongside the participants in Groups 1 and 2.

As participants in Groups 1 and 2 will be recruited at the point of either diagnosis or relapse, any standard investigations their clinician deems necessary for their diagnostic evaluation within NHS protocols will also be performed. Following recruitment, all participants (Groups 1-3) will undergo the first study appointment, the experimental combined MR imaging protocol. Alongside this, participants in Groups 1 and 2 only will undergo the DXA imaging scan and the bone biomarker blood and urine tests. Once both imaging appointments have been completed, all participants will be asked to complete a short questionnaire relating to the MRI imaging and Groups 1 and 2 will be asked to complete this questionnaire for the DXA imaging too; no questionnaires are to be completed for the bone biomarker test. Groups 1 and 2 participants will also be asked to complete a validated quality of life questionnaire.

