6. PARTICIPANT IDENTIFICATION

6.1. Study Participants

Patients with newly diagnosed or relapsed myeloma, smouldering myeloma (Group 1; n=34), MGUS (intermediate or high risk) (Group 2; n= 13), and healthy age-matched volunteers (Group 3; n=13) are eligible to be included in the trial if they meet the following criteria:

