7.1. Recruitment

Newly diagnosed or newly relapsed myeloma patients (Group 1) with or without X-ray detectable bone disease, Smouldering myeloma and high or intermediate MGUS patients (Group 2), without X-ray detectable bone disease, will be invited to participate. Healthy age-matched volunteers (Group 3) will be recruited from the local myeloma support group community, (for example patients' partners).

Patients will be identified by the clinician or clinical care team. Potential patients will then be approached by the myeloma clinical research team during a routine clinic visit and given information about the study. If the participant is interested then they will have a further detailed discussion about the study with a research coordinator and will be given the participant information sheet to take home. They will return to clinic after a minimum period of 24 hours, and will have the opportunity to ask any questions regarding the study. If the participant remains happy to enter the study, their informed consent will be obtained by the investigator prior to initiating any study related investigations.

We anticipate a 10% screen failure for group 1 participants, primarily due to pain and contraindications for MRI. We anticipate 5% screen failure rate for group 2 participants due to contraindications for MRI scan. Both of these figures have been incorporated in the sample size calculations.

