7.3.3 Recruitment Logs

Participants deemed eligible after screening will be registered on to the study and be given a unique Study ID. Registered participants will be recorded on an enrolment log with information including Study ID, Date of Birth, Initials and hospital number as well as date of consent. No personal information, which may identify the participant, should be included on the recruitment log.

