7.7. Discontinuation/Withdrawal from Study

Each participant has the right to withdraw from the study at any time. In addition, the Investigator may discontinue a participant from the study at any time if the Investigator considers it necessary for any reason including:

- Pregnancy
- Ineligibility (either arising during the study or retrospectively having been overlooked at screening)
- Significant protocol deviation
- Significant non-compliance with treatment regimen or study requirements
- Withdrawal of Consent
- Loss to follow up

For participants who are withdrawn from the study, identifiable data or tissue already collected with valid consent would be retained and used in the study. No further data or tissue would be collected or any other research procedures carried out on or in relation to the participant. All withdrawal information including reason for withdrawal will be recorded on the Withdrawal CRF.

Every effort will be made to replace participants who have been withdrawn from the study.

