10. STATISTICS AND ANALYSIS

10.1. Description of Statistical Methods

The primary outcome of this study is the ADC in patients with and without a complete/very good partial response to therapy at follow-up. It is estimated that for group 1, between baseline and follow-up, 85% of individuals will reduce their myeloma burden from 40% to 10% or less compared with 15% who will achieve a partial response (a ratio of 0.15).

A previous study in a similar population the median ADC score improved from 0.79 (IQR 0.66 to 1.26) to 1.5 (IQR 0.88 to 1.83) in those with a complete/very good partial response compared with 0.66 (IQR 0.52 to 0.87) to 0.75 (0.51 to 1.27) in those with a partial response [Latifoltojar BJH 2016].

To detect a similar difference in this cohort with an ADC in complete/ very good partial response of 1.5 at follow-up vs. 0.75 in those with a partial response, a conservative estimated SD of 0.5, and a ratio of 0.15 will require 34 individuals in total (29 vs. 5) with 80% power and 0.05 type I error. We will, therefore, aim to recruit a total of 37 (31 vs. 6) participants for the study to allow for a dropout rate of 5%.

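### Section 10.1 plans to recruit 37 myeloma patients to absorb 5% dropout, but every stated Group 1 target is 34; the screen-failure claim and the group for smouldering myeloma do not reconcile either

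*Combined protocol and SAP*

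**What the plan says.** **Group 1 size.** Section 10.1 takes follow-up ADC means of 1.5 and 0.75, an SD of 0.5, a ratio of 0.15, 80% power and a 0.05 type I error, and arrives at 34 patients (29 vs. 5). It then says the study will "aim to recruit a total of 37 (31 vs. 6) participants for the study to allow for a dropout rate of 5" per cent. The synopsis gives "Group 1- Myeloma- 34" out of 60. Section 5 says 60 subjects will be recruited, as "Group 1: Myeloma, (n=34), Group 2: MGUS, (n=13) and Group 3: Healthy age-matched volunteers, (n=13"). Section 6.1 repeats 34.

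**Withdrawals.** Section 7.7 says "Every effort will be made to replace participants who have been withdrawn from the study". It gives no number and no time limit.

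**Screen failure.** Section 7.1 expects 10% in Group 1 and 5% in Group 2 and adds: "Both of these figures have been incorporated in the sample size calculations". Section 7.3.3 says "Participants deemed eligible after screening will be registered on to the study".

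**Smouldering myeloma.** Section 6.1 reads "Patients with newly diagnosed or relapsed myeloma, smouldering myeloma (Group 1; n=34), MGUS (intermediate or high risk) (Group 2; n= 13"). Section 7.1 reads "Smouldering myeloma and high or intermediate MGUS patients (Group 2), without X-ray detectable bone disease". Section 6.2 lists the diagnosis in one bullet with MGUS, under criteria that cover Groups 1 and 2 together, and assigns no group.

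**The concern.** The 34 in Section 10.1 is the number needed before dropout. The same 34 appears elsewhere as the number to be recruited. If 34 is the recruitment target, the 5% allowance is missing; if 37 is, three other sections and the total of 60 are wrong. Nobody could later say whether the study met its planned size.

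The smaller side of the primary comparison has about five patients, so losing one there matters more than losing two or three from the total.

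The smouldering conflict concerns who is analysed. The primary comparison classifies patients by response to therapy, and Section 10.2 compares Groups 1 and 2 by ANOVA and ANCOVA. As written, the same patient could be counted in either group. If that is settled only at analysis, the choice could be influenced by the data.

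**Working it through.** **Inputs.** From Section 10.1: difference 1.5 − 0.75 = 0.75; SD 0.5; ratio 0.15 (smaller to larger group); type I error 0.05; power 80%; dropout 5%. Sidedness is not stated; two-sided is assumed. From Section 7.1: screen failure 10% and 5%. From the synopsis and Sections 5 and 6.1: 34 + 13 + 13 = 60.

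**1. Reproducing 34.** For a two-sample t test, power comes from the noncentral t distribution with n1 + n2 − 2 degrees of freedom and noncentrality 0.75 / (0.5 × √(1/n1 + 1/n2)). With n2 = 0.15 × n1, the smallest n1 that reaches 80% is 29. Then n2 = 4.35, rounded up to 5, total 34. This matches the plan.

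**2. Reproducing 37.** Dividing each response group by 0.95: 29/0.95 = 30.5, up to 31; 5/0.95 = 5.3, up to 6; total 37. This matches the plan's 31 vs. 6. Dropout alone therefore explains the step from 34 to 37.

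**3. Testing the screen-failure claim.** Inflating 34 for 10% gives 34/0.90 = 37.8, so 38, not 37. Applying both allowances gives 34/(0.95 × 0.90) = 39.8, so 40. Neither figure is in the plan, and Section 10.1 has no Group 2 calculation. Registration follows screening, so screen failure changes how many must be approached. Registering 37 would need 37/0.90 = 41.1, so 42. The plan gives no number to approach.

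**4. Patients remaining if 5% are lost and not replaced.** 34 × 0.95 = 32.3, about 32. 37 × 0.95 = 35.15, about 35.

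**5. Power at fixed splits** (same t test):

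| Split | Total | Power |
|---|---|---|
| 31 vs. 6 | 37 | 90.5% |
| 29 vs. 5 | 34 | 85.2% |
| 27 vs. 5 | 32 | 84.6% |
| 28 vs. 4 | 32 | 77.5% |

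**6. Power with a random split.** The number without CR/VGPR is not fixed in advance. Treat it as Binomial(N, 0.15) and average the power:

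| Evaluable N | Average power | Chance of fewer than 5 without CR/VGPR |
|---|---|---|
| 32 | about 78% | 46% |
| 34 | about 81% | 41% |
| 35 | about 82% | 38% |

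**7. Chance of keeping at least 34,** with independent 5% loss and no replacement. If 34 are recruited, all must stay: 0.95^34 = 17%. If 37 are recruited, at most 3 may be lost: P(Binomial(37, 0.05) ≤ 3) = 89%.

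**8. Smouldering myeloma.** The documents give no count, so the effect cannot be computed. For illustration only, suppose some of the 34 have smouldering disease and no therapy response to classify. With an 85/15 split of the remainder, 4 such patients leave 30 and about 81% power, and 6 leave 28 and about 78%.

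**The case against.** The best defence is that little power is lost. At the plan's own split, power moves from 85.2% to 84.6%, still above 80%. The 77.5% figure belongs to one unfavourable split, and most of the risk of a very small comparison group comes from the 85/15 split, which is present with no dropout at all. All of that stands, and it limits the point to a moderate one.

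Next, Section 7.7 intends replacement, so 34 could be read as a completer target and the 17% as a worst case. It is a worst case. But an intention without a number does not explain why Section 10.1 states 37, and Section 5 presents its 34 as patients to be recruited.

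Third, pain or an MRI contraindication might surface only at the scanner, after registration, so screen failure could reduce the registered number. Section 6.3 makes these exclusion criteria and Section 7.3.3 puts eligibility before registration. A patient lost at the scanner is then a dropout, not a screen failure.

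Fourth, smouldering allocation is a grouping issue and not arithmetic. That is fair as a label. It belongs here because it decides who counts toward the 34.

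Finally, the documents do not show whether the sponsor meant 34 or 37, and 34 without replacement averages about 78%, under the stated 80%. That is also fair: whichever figure is kept must carry its own power.

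**Conclusion.** The concern holds and should be fixed. Both 34 and 37 reproduce exactly; the error is that 37 was not carried into the group targets, or that 34 was not carried back into Section 10.1. The screen-failure sentence has no supporting calculation, and Sections 6.1 and 7.1 contradict each other on smouldering myeloma.

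The cost in power is modest: under one point at the plan's split, and about four points (78% against 82%) when the split is random. These figures assume a two-sided t test, the plan's difference and SD, independent 5% loss and no replacement. The more serious consequence is that the planned size and membership of Group 1 cannot be read from the plan.

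**What to change.** 1. **Let one Group 1 figure govern.** The cheaper route, and the one preferred here, is to restate Section 10.1 as 34 recruited, with about 32 expected to be evaluable if withdrawals are not replaced. Give the matching power (84.6% at 27 vs. 5; about 78% averaged over the split), state sidedness, and refer to the replacement rule in Section 7.7. If the sponsor keeps 37, change the synopsis and Sections 5 and 6.1 to 37 and the total to 37 + 13 + 13 = 63.
2. **Correct or remove the screen-failure sentence in Section 7.1,** or show the calculation and the number to be approached in each group.
3. **Reconcile Sections 6.1 and 7.1** so that smouldering myeloma sits in one group, and make Section 6.2 agree. Do this before analysis.
4. **State who enters the response comparison:** Group 1 patients who received therapy after baseline.

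The first route is wording only and needs no extra patients. Keeping 37 adds three Group 1 participants, each with baseline and follow-up MR, DXA and biomarker tests.

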10.2. Analysis of Outcome Measures/Endpoints

Differences in baseline characteristics between participants groups (1, 2 and 3) will be compared using chisquare test for categorical variables and one-way analysis of variance (ANOVA) for continuous variables.

To assess ability of MRI to detect improvement or deterioration in tumour burden and bone health, differences between DW-MRI data imaging from the two time-points (baseline and 6 months follow up) will be tested using paired t test. In addition, ADC, total spine 'hole' and 'collapse' volume and FSA trabecular wall thickness will be compared with bone mineral density at the lumbar spine, total hip and femoral neck T score and g/cm², serum CTX-1 and PINP using correlation analysis in group 1 (complete/very good partial response vs. partial response) and in group 2. These models will be run at baseline and at follow-up.

Differences between groups 1 and 2 in experimental MR measurements at follow up will be estimated using one-way analysis of variance (ANOVA) and analysis of covariance (ANCOVA) when baseline values and potential confounders (including gender, age and body mass index (BMI)) are adjusted. Endpoints will be checked for normality and transformed if possible.

In order to determine the change in EQ-5D throughout the study, repeated measured linear regression analysis will be used where EQ-5D at baseline and follow up will be included as outcome and group as exposure.

Finally, a descriptive analysis of the novel MR imaging scan questionnaire will be conducted to understand participant's experience with the new technique.

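### Section 10.2 splits the Group 1 correlations by response, even at baseline, and gives no pooled estimate: the partial-response stratum (about 5 patients) is uninformative, and baseline should not be split by a later outcome

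*Combined protocol and SAP*

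**What the plan says.** Section 10.2 (Analysis of Outcome Measures/Endpoints) states that "ADC, total spine 'hole' and 'collapse' volume and FSA trabecular wall thickness will be compared with bone mineral density". The BMD comparators cover three sites (lumbar spine, hip, femoral neck), each expressed both as a T score and in g/cm²; two serum markers, CTX-1 and PINP, are added. The plan is to do this "using correlation analysis in group 1 (complete/very good partial response vs. partial response) and in group 2". On timing, the section adds: "These models will be run at baseline and at follow-up". It gives no pooled Group 1 correlation, no type of correlation, no target precision and no multiplicity rule.

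Response is a follow-up status. Section 10.1 says: "The primary outcome of this study is the ADC in patients with and without a complete/very good partial response to therapy at follow-up". The same section expects a split of 85% to 15%, which it turns into 29 and 5 patients, and then 31 and 6 after allowing 5% dropout.

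Section 7.4.1 (item 3, the MR imaging protocol) describes the correlation of MR bone density, lytic volume and collapse volume with DXA without naming any strata. That overall estimate is not carried into Section 10.2.

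**The concern.** Whether an MR bone measure tracks DXA or a turnover marker at one visit is a cross-sectional question. It needs no knowledge of response. Splitting Group 1 by response has three costs:

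- One stratum is too small to say anything.
- At baseline, patients are sorted by something that has not yet happened.
- Patients who are neither complete/very good partial nor partial responders have no place in the analysis. Section 6.1 puts smouldering myeloma in Group 1 (Section 7.1 can be read as placing it with Group 2). Section 5 lets follow-up fall at progression or relapse. Some patients may have less than a partial response, be untreated, or be lost before follow-up. Their baseline MR and reference values are valid but would go unused.

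At stake is the comparison of the MR bone measures with the listed correlate endpoints. Read literally, the plan reports it in pieces and never as one Group 1 estimate.

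**Working it through.** **Stratum sizes.** Inputs from Section 10.1: difference 1.5 - 0.75 = 0.75, SD 0.5, ratio 0.15, 80% power, type I error 0.05 (two-sided assumed). A noncentral-t calculation with fractional allocation gives 29 in the larger group and 0.15 × 29 = 4.35, rounded up to 5, in the smaller: total 34, as stated. Dropout by stratum: 29/0.95 = 30.5, so 31; 5/0.95 = 5.3, so 6; total 37, as stated.

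**Precision.** The documents give no expected correlation, so r = 0.5 is assumed for illustration.

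- Critical |r| = t/√(n - 2 + t²), with t the 97.5% point on n - 2 df. For n=5: 3.182/√(3 + 10.13) = 0.88.
- 95% CI = tanh(atanh r ± 1.96/√(n - 3)). For n=5, r=0.5: tanh(0.549 ± 1.386) = -0.68 to 0.96.
- Power comes from 100,000 simulated bivariate-normal samples.

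| Set | n | Critical \|r\| | 95% CI if r=0.5 | Power if true r=0.5 |
|---|---|---|---|---|
| Partial response | 5 | 0.88 | -0.68 to 0.96 | 13% |
| Partial response, with dropout allowance | 6 | 0.81 | -0.52 to 0.93 | 17% |
| Complete/very good partial response | 29 | 0.37 | 0.16 to 0.73 | 81% |
| All Group 1 | 34 | 0.34 | 0.19 to 0.72 | 87% |
| Group 2 | 13 | 0.55 | -0.07 to 0.82 | 43% |

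At a true r of 0.7, power is 27% with n=5 and 82% with n=13.

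**Chance variation in the small stratum.** If 15% of 34 are partial responders (mean 5.1), the binomial probability of 4 or fewer is 41%, and of 3 or fewer 23%. With 3, n - 3 = 0 and the Fisher interval does not exist.

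**Contrast between strata.** The SE of the difference in Fisher z is √(1/26 + 1/2) = 0.73. If r = 0.6 in the 29 (z = 0.693), the partial-response r would have to be at or below tanh(0.693 - 1.438) = -0.63 to differ at 5%.

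**Bias from conditioning on later response.** A simulation sorted patients by a latent normal response score, with the lowest 15% as partial responders. The score was given assumed weights of 0.3 or 0.5 on one measure, or 0.3 on one and ±0.3 on the other. A true baseline r of 0.5 became 0.46 to 0.51 in the large stratum and 0.40 to 0.53 in the small one.

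**Number of correlations.** The text names 4 MR measures and 3 BMD sites in two units plus 2 markers = 8 comparators.

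- As written: 4 × 8 × 3 strata × 2 visits = 192.
- With T score and g/cm² counted once: 4 × 5 × 3 × 2 = 120.
- With Group 1 also pooled: 4 × 5 × 2 groups × 2 visits = 80.

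At 0.05, with every correlation null (a worst case), these give 9.6, 6 and 4 expected chance positives.

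**The case against.** The strongest reply is that most of the information survives the split. The stratum of 29 has nearly the precision of the pooled 34. Group 2 can show a correlation near 0.7. This stands: a reader might infer that the correlations as a whole are uninformative, and the table does not support that.

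A reader might also infer that these are the study's only check against a reference and that the primary objective rests on them. The documents do not support that either. Section 7.4.1 also plans to correlate MR marrow infiltration with biopsy (and PET-CT where performed) and to repeat MR bone measurements for reproducibility. Section 10.1 defines and powers the primary outcome on ADC by response.

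Nor can serious bias from the baseline split be claimed. Under the assumed links it is small; the loss is in interpretability and discarded data.

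The count of 192 is the highest reading, and Section 10.2 attaches no significance rule to these correlations. A mass of zero hole and collapse volumes in Group 2 might be inferred from its recruitment as "high or intermediate MGUS patients (Group 2), without X-ray detectable bone disease". But the background says MR detects lesions that X-ray misses, and no zero fraction is given, so this is only a possibility.

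Finally, the parenthesis about response is terse, and separate correlations per stratum is the natural reading but not the only one. If something else is meant, the section still needs to say so and to state the pooled estimate.

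**Conclusion.** The point holds in a limited form. By the plan's own expected split, correlations in the partial-response stratum, and any comparison between response strata, are uninformative. With 5 patients the interval around r = 0.5 runs from -0.68 to 0.96, and 6 patients hardly help. Splitting the baseline data by later response serves no stated purpose and leaves out patients in neither category. The documents do not give the number of such patients; Section 10.1 allows for none, since its 85% and 15% sum to 100%. The missing element is a pooled Group 1 estimate.

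For most of Group 1 the gain in precision from pooling is modest (CI 0.16 to 0.73 becoming 0.19 to 0.72). The larger gain is a single interpretable estimate that uses every valid pair. The figures assume bivariate normality, an illustrative r and 34 analysable Group 1 patients. This is a cheap improvement, not a flaw that undermines the study.

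**What to change.** Amend Section 10.2 as follows:

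- Estimate each correlation in all of Group 1, and separately in Group 2, at each visit, with a 95% CI.
- Do not split by response at baseline.
- At follow-up, report the pooled estimate. Add a response-adjusted (partial) correlation, or a scatter plot marked by response, as a descriptive supplement. Response is known by then and may move both measures, so showing it is reasonable.
- Use BMD in g/cm² only, because T score re-expresses the same measurement.
- State the type of correlation, with Spearman for hole and collapse volumes if many values are tied at zero.

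The cost is wording only: no extra patients, visits or scans. The small downside is that the pooled follow-up estimate assumes a common slope across response categories. The marked plot gives a visual check, although with about 5 partial responders it cannot test that assumption.

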4. OBJECTIVES AND OUTCOME MEASURES/ENDPOINTS

	Objectives	Outcome Measures
Primary	To develop and pilot test a novel MR imaging protocol with the aim to accurately: 1. Quantify tumour burden 2. Quantify bone loss	Novel imaging based endpoints: 1. DW-MRI: ADC change (Pawlyn et al, 2016) 2. Total spinal 'hole' volume 3. Total spine 'collapse' volume 4. FSA: trabecular wall thickness (Rafferty et al, 2016) Correlate endpoints: Bone density (DXA imaging) Serum CTX-1 Serum P1NP Further experimental serum biomarkers of myeloma bone disease
Secondary	To pilot test a novel MR imaging protocol with the aim to accurately: 1. Detect longitudinal changes in tumour load with therapy 2. Detect longitudinal changes in bone	1 and 2 - Repeat quantification of endpoint parameters after induction therapy and best response achieved by IWMG criteria or at treatment failure

microarchitecture with	3 – Analyse participants quality of
therapy	life using data from the EQ-5D-5L
3. Assess participants	questionnaire
Quality of Life (EQ-5D)	
throughout the study	
4. Assess participants experience of the novel MR imaging scan	4- Analyse participants experience of the novel MR imaging using data from MRI/DXA scanning questionnaire

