Participants in Groups 1 and 2 will undergo a further experimental MR scan, DXA imaging and bone biomarker blood tests at 6 months or at time of progression/relapse, whichever is sooner (but no sooner than 3 months after the initial investigations) to evaluate change in disease burden and bone loss. The reason participants in Group 2 will be rescanned at 6 months even if they have not progressed to myeloma and are not on therapy, is to address the following questions, 1. Can trabecular thinning progression be detected with time in MGUS patients whose paraprotein is stable or rising? 2. Reproducibility test: In

patients with a stable paraprotein, if assumed that trabecular thickness is stable or at most slightly worse over 6 months, is trabecular quantification reproducible over time?

In addition to this, all participants in Groups 1 and 2 will also be asked to complete the short questionnaire relating to the MRI and DXA imaging and the quality of life questionnaire for assessment of patient experiences of both imaging procedures, both at the first study appointment and at the 6 month follow up appointment. Standard of care clinical investigations will be repeated within NHS protocols if clinically indicated. Results of relevant NHS diagnostic investigations, clinical outcomes and survival data will be collected and stored.

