7.5. Subsequent Visits

For Groups 1 and 2, a follow up visit will take place 6 months after the baseline assessment.

Tests 1, 2, 3 and 4 from baseline assessment will be repeated in exactly the same way for both Group 1 and 2.

Repeat data collection (on intervening treatment and disease monitoring results, from hospital records) will be performed.

No subsequent data collection or assessment will be performed on Group 3 (Healthy volunteers) at 6 months, as the only purpose of their inclusion is to establish reproducibility and a normal range for experimental MR output data. Therefore, group 3 participation stops at the end of their baseline assessments.

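### The EQ-5D model in Section 10.2 is meant to measure change but names no visit or group-by-visit term; fitted literally, it estimates a group difference averaged over the two visits

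*Combined protocol and SAP*

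**What the plan says.** Section 10.2 of the combined protocol and SAP states the purpose of the quality-of-life analysis: "In order to determine the change in EQ-5D throughout the study". The method is a linear regression for repeated measurements, in which "EQ-5D at baseline and follow up will be included as outcome and group as exposure". Group is the only explanatory term named.

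Section 5 collects the questionnaire from Groups 1 (myeloma) and 2 (MGUS) "both at the first study appointment and at the 6 month follow up appointment", so there are two time points. The healthy volunteers are seen once: Section 7.5 states that "group 3 participation stops at the end of their baseline assessments".

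The synopsis and Section 4 list quality of life as secondary objective 3. They say only that it will be assessed over the course of the study and that EQ-5D-5L data will be analysed. Neither gives a model.

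**The concern.** The stated purpose and the stated model do not match. Handling repeated measurements in a regression deals with the correlation between two values from the same person. In a mixed model or GEE it does not put visit on the right-hand side; the analyst has to list it. With group alone, no parameter represents change.

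Two things could go wrong. A quality-of-life gap already present at baseline between myeloma and MGUS could be reported as the result of an analysis of change. And a real shift over six months could be missed, because a change shared by both groups leaves the group coefficient where it was and a change in one group is diluted.

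**Working it through.** The documents give no EQ-5D mean, standard deviation, effect size or power, so there is no figure of the plan's own to reproduce. The check is algebraic, with an illustration.

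**Inputs from the documents.** Two visits for Groups 1 and 2 (Sections 5 and 7.5); planned sizes 34 and 13 (Section 5); group as the only named term (Section 10.2).

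**Assumed inputs, for illustration only.** Baseline means of 0.60 in Group 1 and 0.80 in Group 2, and the changes in the table below.

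**Algebra.** Let d0 and d1 be the Group 1 minus Group 2 differences at baseline and follow-up, and D = d1 - d0 the difference in change. With complete data, a model containing only group compares each group's average over the two visits:

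group coefficient = (d0 + d1)/2 = d0 + D/2

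So the coefficient holds the whole baseline gap plus half the difference in change. If both groups change by the same amount, D = 0 and the coefficient stays at d0. The intercept takes up half of the reference group's change, but a single fit contains no baseline value to compare it with.

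**Numbers put in** (d0 = 0.60 - 0.80 = -0.20 throughout):

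| Change, Group 1 | Change, Group 2 | d1 | Group coefficient (d0 + d1)/2 | True difference in change D |
|---|---|---|---|---|
| 0 | 0 | -0.20 | -0.20 | 0 |
| +0.10 | +0.10 | -0.20 | -0.20 | 0 |
| -0.10 | -0.10 | -0.20 | -0.20 | 0 |
| +0.10 | 0 | -0.10 | -0.15 | +0.10 |
| +0.20 | -0.20 | +0.20 | 0.00 | +0.40 |

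In the first three rows the coefficient is identical, although the groups stay still, improve or worsen. In the fourth row it shifts by 0.05, half of D = 0.10. In the last row the groups move in opposite directions and the coefficient is zero.

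**With visit terms.** Write EQ-5D = a + b(Group 1) + c(visit) + d(Group 1 x visit), with Group 2 as reference. Then c is the Group 2 change, c + d is the Group 1 change, and d = D. In the fourth row c = 0 and d = 0.10; in the last row c = -0.20 and d = 0.40.

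Fitting both models by GEE with exchangeable correlation to constructed data for 34 and 13 participants agreed with the algebra. The group-only coefficient had the same size for no change, for +0.20 in both groups and for -0.10 in both groups, and it was zero for +0.20 against -0.20. Only the model with visit terms returned the changes.

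**Precision of the target contrast.** With 34 and 13 complete pairs, the standard error of D is sqrt(1/34 + 1/13) = 0.326 times the SD of change. At 80% power and two-sided 0.05, the detectable difference is (1.960 + 0.842) x 0.326 = 0.91 SD of change, or 0.93 using the t distribution. The documents do not give that SD.

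**The case against.** The strongest reply is that Section 10.2 offers a sentence of prose and not a model formula. In a repeated-measures ANOVA, or a regression with the two visits as joint outcomes, visit is a within-person factor by construction and the exposure named is just the between-person factor. Change could then be derived, and the declared purpose favours that reading. This stands as far as intent goes: the documents do not show that the sponsor chose a group-only model deliberately, and the defect may be under-specification. It does not remove the problem. The same section spells out a paired comparison of the two time points for the DW-MRI data and a baseline-adjusted ANCOVA for the MR measurements, but gives neither for EQ-5D. Even on the generous reading, the text does not say whether the target is change within each group, the difference in change, or both.

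A reader might also infer that secondary objective 3 cannot be answered at all. The documents do not support that. The objective is to assess quality of life through the study, and a between-group comparison over both visits covers part of it. Change as the target appears only in Section 10.2, so the mismatch lies within that section.

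Nor do the documents say that Group 3 enters this model. Section 5 asks only Groups 1 and 2 for the quality-of-life questionnaire, and Appendix A marks EQ-5D as not applying to healthy volunteers. Sections 7.4.1 and 7.4.2, taken together, read the other way. What is certain is that Group 3 has no follow-up and so can give no change.

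**Conclusion.** The point holds as a mismatch between a stated target and a stated model. Read literally, with complete data on two visits, the group coefficient is the between-group EQ-5D difference averaged over visits. It is blind to equal change and shows only half of any difference in change. That result is algebraic and does not depend on the 0.60 and 0.80 means, which are assumptions used to show the size. If the sponsor did intend a visit factor, the analysis may be sound but the plan does not record it.

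The consequence is modest. EQ-5D is a secondary objective in an observational pilot, no power claim rests on it, and the primary outcome and sample size are untouched. The wording should still be corrected before analysis, because the data needed for the right model are already being collected.

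**What to change.** In Section 10.2, replace the EQ-5D sentence with a model of EQ-5D on visit, group and group-by-visit, restricted to Groups 1 and 2, with a participant random intercept or an equivalent within-person correlation structure. Name the contrasts: change within each group, and the between-group difference in change, each with a 95% confidence interval. Give the reason for leaving out Group 3, which is already in Section 7.5: "No subsequent data collection or assessment will be performed on Group 3". Bring Sections 5, 7.4.1, 7.4.2 and Appendix A into line on whether healthy volunteers complete the questionnaire at baseline.

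Borrowing the ANCOVA that 10.2 uses for the MR measurements would not be an adequate substitute. It gives no within-group change, and in non-randomised groups with a baseline gap it targets a different quantity from the difference in change.

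The cost is a sentence or two in 10.2 and a consistency edit elsewhere. No extra data, visits or participants are needed.
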